5.5. Prophylactic and Supportive Medications

At least 24 hours prior to Cycle 1 Day 1, the following treatments should be started:

- Valacyclovir 500 mg PO daily (or equivalent antiviral), continuing for the duration of treatment (additional prophylaxis is at the Investigator's discretion) for varicella zoster prevention while on carfilzomib-based therapy
- Pantoprazole 40mg PO daily, or other oral proton-pump inhibitor to prevent peptic disease for the duration of treatment with dexamethasone
- Aspirin (enteric-coated) PO daily at the standard prophylactic dose continuing for the duration of treatment with lenalidomide and dexamethasone. Other antiplatelet or anticoagulation medications may be used in cases of intolerance to aspirin at the Investigator's discretion.

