- 3.2.8. Subjects' medication list such a herbal medicines (*e.g.*, St. John's wort), vitamins, and supplements will be reviewed before starting first dose of KRT-232 (AMG 232) and at each clinic visit. Any potential drug interactions will be brought and discussed with the Principle Investigator. Use of any known CYP3A4 substrates with narrow therapeutic window (such as alfentanil, astemizole, cisapride, dihydroergotamine, pimozide, quinidine, sirolimus, or terfanide) within the 14 days prior to receiving the first dose of KRT-232 (AMG 232) is not permitted. Other medications (such as fentanyl and oxycodone) may be allowed per investigator's assessment/evaluation.
- 3.2.9. Treatment with medications known to cause QTc interval prolongation within 7 days of study day 1 is not permitted unless approved by the sponsor. Use of ondansetron is permitted for treatment of nausea and vomiting.

- 3.2.10. Current use of warfarin, factor Xa inhibitors and direct thrombin inhibitors.
Note: Low molecular weight heparin and prophylactic low dose warfarin are permitted. PT/PTT must meet the inclusion criteria. Subjects taking warfarin must have their INR followed closely.
- 3.2.11. Uncontrolled intercurrent illness including, but not limited to, ongoing or active infection, symptomatic congestive heart failure, unstable angina pectoris, cardiac arrhythmia, or psychiatric illness/social situations that would limit compliance with study requirements.
- 3.2.12. Subjects with myocardial infarction within 6 months of study day 1, symptomatic congestive heart failure (New York Heart Association (NYHA) Class III and higher), unstable angina, or cardiac arrhythmia requiring medication are excluded.
- 3.2.13. Subjects with GI tract disease causing the inability to take oral medication, malabsorption syndrome, requirement for intravenous alimentation, prior surgical procedures affecting absorption, uncontrolled inflammatory GI disease (e.g., Crohn's disease, ulcerative colitis).
- 3.2.14. Subjects with history of bleeding diathesis.
- 3.2.15. Subjects with active infection requiring IV antibiotics within 2 weeks of study enrollment (day 1) are excluded.

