+ 4	180 mg/day PO x 7 days out of 28 day cycle
+ 5	240 mg/day PO x 7 days out of 28 day cycle

If dose-de-escalation is needed for Dose level 1, Dose level -1 is defined as 30 mg/day x 7 days out of 28 day cycle.

There should be no dose modifications of KRT-232 (AMG 232) and KRd during the DLT-evaluable period (Cycle 1). Subjects requiring dose-reductions during the DLT-evaluable period will be considered a DLT.

Part B (Dose-expansion scheme)

After determination of the KRT-232 (AMG 232) MTD or proven tolerability of the highest planned dose, and a goal of 10 additional subjects will be treated in the Part 2 dose expansion in combination with KRd. The primary objective of this dose-expansion phase is to confirm the safety and tolerability of KRT-232 (AMG 232) + KRd at the MTD and tentative RP2D in a goal

of 10 subjects with relapsed and/or refractory multiple myeloma. The tentative RP2D will be determined based on the review of safety data at the MTD.

During the dose-expansion phase, subjects removed from study after Cycle 1 based on the *TP53* mutation and/or deletion status will be replaced to ensure that a goal of 10 subjects with *TP53* wild-type status are enrolled in the dose-expansion cohort.

The subject will be requested to maintain a medication diary of each dose of medication. The medication diary will be returned to clinic staff at the end of each course.

KRT-232 (AMG 232)

The following medications and/or therapies should not be administered within the timeframes specified prior to enrollment and during the study (unless otherwise specified below):

- Antitumor therapy (chemotherapy, antibody therapy, molecular targeted therapy, retinoid therapy, hormonal therapy, or investigational agent) within 21 days of study day 1; concurrent use of hormone deprivation therapy for hormone-refractory prostate cancer or breast cancer and continuation of previous hormone therapy in breast cancer subjects are permitted.
- Treatment with immune modulators including, but not limited to, corticosteroids, cyclosporine and tacrolimus within 3 weeks prior to enrollment, except for a corticosteroid dose equivalent to dexamethasone of ≤ 4 mg/day
- Therapeutic or palliative radiation therapy within 4 weeks of KRT-232 (AMG 232) day 1.

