- All herbal medicines (e.g., St. John's wort), vitamins, and supplements consumed by the subject within the 30 days prior to receiving the first dose of KRT-232 (AMG 232), and continuing use, if applicable, will be reviewed by the Principal Investigator and the sponsor.
- Use of any known CYP3A4 substrates with narrow therapeutic window (such as alfentanil, astemizole, cisapride, dihydroergotamine, pimozide, quinidine, sirolimus, or terfanide) within the 14 days prior to receiving the first dose of KRT-232 (AMG 232). Other medications (such as fentanyl and oxycodone) may be allowed per investigator's assessment/evaluation.
- Use of any known CYP2C8 substrates with a narrow therapeutic window within the 14 days prior to receiving the first dose of KRT-232 (AMG 232)
- Treatment with medications known to cause QTc interval prolongation within 7 days of study day 1 unless approved by the sponsor. Use of ondansetron is permitted for treatment of nausea and vomiting. Systemic anticoagulation therapy, with warfarin, direct thrombin inhibitors, indirect thrombin inhibitors and direct factor Xa inhibitors, within 14 days or 5 half-lives (whichever is longer) of day 1. Low molecular weight heparin and prophylactic low-dose warfarin are permitted.
- Autologous stem cell transplantation at least 12 weeks prior to starting KRT-232 (AMG 232) + KRd
- Allogeneic stem cell transplantation at least 24 weeks prior to starting KRT-232 (AMG 232) + KRd, and these subjects must also NOT have moderate to severe active acute or

chronic graft versus host disease (GVHD).

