- **Hydration** - Adequate hydration is required prior to dosing in Cycle 1, especially in subjects at high risk of tumor lysis syndrome or renal toxicity. The recommended hydration includes both oral fluids (30 mL per kg at least 48 hours before Cycle 1, Day 1) and intravenous fluids (250 mL to 500 mL of appropriate intravenous fluid prior to each dose in Cycle 1). If needed, give an additional 250 mL to 500 mL of intravenous fluids following carfilzomib administration. Continue oral and/or intravenous hydration, as needed, in subsequent cycles. Monitor subjects for evidence of volume overload and adjust hydration to individual subject needs, especially in subjects with or at risk for cardiac failure.
- **Electrolyte Monitoring** - Monitor serum potassium levels regularly during treatment with carfilzomib.
- **Premedications** - Premedicate with the recommended dose of dexamethasone for monotherapy or the recommended dexamethasone dose if on combination therapy. Administer dexamethasone orally or intravenously at least 30 minutes but no more

than 4 hours prior to all doses of Carfilzomib during Cycle 1 to reduce the incidence and severity of infusion reactions. Reinstate dexamethasone premedication if these symptoms occur during subsequent cycles.

- Thromboprophylaxis - Thromboprophylaxis is recommended for subjects being treated with the combination of carfilzomib with dexamethasone or with lenalidomide plus dexamethasone. The thromboprophylaxis regimen should be based on an assessment of the subject's underlying risks.
- Infection Prophylaxis - Consider antiviral prophylaxis for subjects being treated with carfilzomib to decrease the risk of herpes zoster reactivation.

Agent Ordering: Carfilzomib is commercially available.

Please refer to the FDA approved package insert for additional information.

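### Section 5.5 leaves the substitute for aspirin open to any anticoagulant, while Section 5.4 rules several classes out around day 1 and on study; the sections need one common rule

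*Combined protocol and SAP*

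**What the plan says.** Section 5.5 introduces its prophylaxis list with "At least 24 hours prior to Cycle 1 Day 1, the following treatments should be started". Aspirin is on that list and continues for as long as lenalidomide and dexamethasone are given. For subjects who cannot take it, "Other antiplatelet or anticoagulation medications may be used in cases of intolerance to aspirin", at the investigator's discretion. No class or dose is excluded, and no other section is cited.

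Section 5.4, under the KRT-232 heading, lists therapies that "should not be administered within the timeframes specified prior to enrollment and during the study", subject to exceptions specified further down. One entry is "Systemic anticoagulation therapy, with warfarin, direct thrombin inhibitors, indirect thrombin inhibitors and direct factor Xa inhibitors, within 14 days or 5 half-lives" of day 1, whichever is longer. The same bullet then permits low molecular weight heparin and prophylactic low-dose warfarin.

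Section 3.2.10 excludes "Current use of warfarin, factor Xa inhibitors and direct thrombin inhibitors", with the same two exemptions.

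Three other places bear on the point:

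- Section 5.6 makes grade 3-4 thrombocytopenia with bleeding above grade 1 a DLT. It leaves out events that have a clear alternative cause, and gives concomitant therapy as an example.
- The lenalidomide thrombocytopenia table in Section 6.4 holds prophylactic anticoagulation when platelets fall below 30,000.
- Section 8.3.1 says of carfilzomib: "The thromboprophylaxis regimen should be based on an assessment of the subject"'s underlying risks. It names no agent.

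**The concern.** A site with an aspirin-intolerant subject can read Section 5.5 alone and choose, say, a direct factor Xa inhibitor. A site that reads Section 5.4 would conclude that this agent should not be used. Both would be following the protocol as they read it.

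Two things are at stake. The first is patient safety: Section 2.6 names thrombocytopenia as an overlapping toxicity to be watched with the KRd (carfilzomib, lenalidomide, dexamethasone) backbone, and the two sections give different answers on which anticoagulants may be given alongside it. The second is how Cycle 1 bleeding is read. Under Section 5.6, bleeding is one of the features that turns grade 3-4 thrombocytopenia into a DLT, and concomitant therapy is one of the reasons for not counting an event. If the anticoagulant depends on which section a site followed, the cause assigned to a bleed may depend on it too.

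**Working it through.** No figure in the plan belongs to this point, so the check is a comparison of texts.

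**Step 1. Compare the rules agent by agent.**

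| Substitute for aspirin | 5.5 | 5.4 | 3.2.10 (at entry) |
|---|---|---|---|
| Low molecular weight heparin | allowed | allowed | allowed |
| Prophylactic low-dose warfarin | allowed | allowed | allowed |
| Warfarin beyond that | allowed | not to be given | excluded |
| Direct thrombin inhibitors | allowed | not to be given | excluded |
| Indirect thrombin inhibitors | allowed | not to be given | not named |
| Direct factor Xa inhibitors | allowed | not to be given | excluded |

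The conflict lies in the last four rows only. Low molecular weight heparin keeps its exemption whatever class it is assigned to. The lists in 5.4 and 3.2.10 also differ slightly: only 5.4 names indirect thrombin inhibitors, and only 5.4 limits the factor Xa entry to direct inhibitors.

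**Step 2. Test whether timing removes the conflict.** The 5.4 bullet has its own window, at least 14 days around day 1, because the longer of 14 days and five half-lives applies. Section 5.5 prophylaxis starts at least 24 hours before Cycle 1 Day 1 and continues through treatment. A substitute begun one day before day 1 is inside a 14-day window. One begun earlier and continued is also in use inside it. So the conflict at treatment start remains even if the 5.4 bar is read as applying before treatment only. For a subject who becomes intolerant of aspirin later, the conflict rests on the phrase in the 5.4 lead-in that extends the list to the study period.

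**Step 3. Trace the consequence to the DLT count.** For a Cycle 1 bleed above grade 1 with grade 3-4 thrombocytopenia, Section 5.6 leaves two outcomes. The event is a DLT, or it is set aside because concomitant therapy is a clear alternative cause. The antithrombotic agent in use is relevant to that choice. The Section 5.6 table acts on single events: 0 of 3 leads to the next dose level, while 1 of 3 leads to three more subjects at the same level. One event counted or not counted can therefore change the next step in a cohort.

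**Step 4. Ask whether the size can be calculated.** That would need the share of subjects intolerant of aspirin, the share of those given a non-exempt agent, and the effect of that agent on bleeding in Cycle 1. The documents give none of the three.

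**The case against.** The strongest reply is that this is an ambiguity with little reach. Several parts of it stand.

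- Low molecular weight heparin and prophylactic low-dose warfarin satisfy every section, so an aspirin-intolerant subject can be managed without breaching anything. This narrows the conflict, but Section 5.5 does not direct sites to those options.
- The 5.4 lead-in allows for exceptions specified below it, and 5.5 comes later. The more natural reading is that the phrase refers to the exceptions inside the list, such as those for hormone therapy and heparin. If 5.5 released every anticoagulant, the narrow exemption in 5.4 would have no on-study purpose. Both readings are possible, which is itself a reason to settle the wording.
- Section 3.2.10 is an eligibility criterion, checked before registration under 4.3.1, and 4.4 allows up to 14 days from registration to treatment. A substitute begun after registration does not by itself breach it.
- Section 8.3.1 is compatible with 5.4 and is not a competing rule.
- Section 6.4 already holds prophylactic anticoagulation below 30,000 platelets, which covers part of the worrying scenario.

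A reader might go further and infer that the choice of anticoagulant determines the thrombocytopenia DLT. The documents do not support that. Grade 4 thrombocytopenia lasting more than 14 days despite holding treatment is a DLT without any bleeding. A Cycle 1 dose reduction is also a DLT. Bleeding clearly due to concomitant therapy is not counted.

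**Conclusion.** The inconsistency is real and should be corrected, in a limited form. It concerns warfarin beyond the prophylactic low dose, thrombin inhibitors and direct factor Xa inhibitors, in subjects who need an alternative to aspirin. For them the protocol permits different treatment at different sites. That bears on bleeding risk and can bear on how a Cycle 1 bleed is classified under Section 5.6. An effect on the maximum tolerated dose is not shown and cannot be quantified from the documents.

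Three stronger readings should be resisted.

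- **All 25-40 subjects are affected.** The rule on aspirin reaches everyone, but the conflict reaches only those who need a substitute. An assumed intolerance of 5-10% would give 0.05 × 25 = 1.25 to 0.10 × 40 = 4 subjects, but that counts users of any substitute, including the exempt ones.
- **The venous event rate measures the problem.** The KRd table in Section 7.1 gives 49/392 = 12.5% (printed as 13%), or about 3.1 to 5.0 of 25-40 subjects. That table covers Cycles 1-12, not the Cycle 1 DLT period. It also concerns subjects who may need treatment for a clot, which the aspirin-intolerance clause does not address.
- **The protocol regards these agents as unsafe with KRT-232.** The visible text gives no reason for the restriction in 5.4.

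The conclusion rests on the visible text. Parts of Section 6 are blacked out and may contain further rules.

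**What to change.** Write one on-study rule for antithrombotic agents and have the other sections refer to it. It should:

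- reconcile Section 5.5 with 5.4 and 3.2.10, using the same class names throughout and repeating the change in the synopsis version of the exclusion criterion;
- say plainly whether the 5.4 restriction applies only around day 1 or throughout the study;
- agree with the hold on prophylactic anticoagulation in the Section 6.4 lenalidomide table.

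Which agents are permitted is for the sponsor to decide; this review proposes none.

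The cost is protocol wording in an amendment. No sample size, analysis or data collection changes, since Section 5.8.1 already requires concomitant drugs to be recorded on the case report form. Showing the antithrombotic agent beside each bleeding event in the DLT listing would be convenient, but it is a preference and not needed to resolve the point.

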5.6. Definition of Dose-Limiting Toxicity

A DLT is defined as any treatment emergent adverse event (TEAE) during the first treatment cycle that does not have a clear alternative cause (e.g., disease under study, concomitant therapy) based on the following criteria using NCI-CTCAE v5.0:

- Hematological toxicity
 - Grade 3 or 4 neutropenia with fever $\geq 38^0$ C lasting > 48 hours
 - Grade 4 neutropenia lasting > 7 days
 - Grade 3 or 4 thrombocytopenia associated with $>$ grade 1 bleeding. Grade 4 thrombocytopenia that persists for > 14 days, despite holding treatment
 - Grade 4 anemia, unexplained by underlying disease
 - Any other grade 4 hematologic toxicity that does not resolve to subject's pre-treatment baseline level within 72 hours
- Non-hematological toxicity
 - Grade ≥ 3 nausea, vomiting or diarrhea lasting longer than 72 hours despite optimal medical support
 - Grade ≥ 3 non-hematological toxicity (excluding increased serum creatinine, or electrolyte abnormalities that are not clinically significant and require no treatment)
 - Any grade 3 electrolyte abnormalities that do not resolve to grade ≤ 2 within 72 hours
 - Grade 3 fatigue persisting > 7 days
 - Grade ≥ 3 acute kidney injury (creatinine $> 3 \times$ baseline or > 4.0 mg/dL) lasting > 72 hours
 - Any other grade 3 or 4 non-hematologic toxicities not predefined above will be considered a DLT.
 - A delay of ≥ 14 days in commencing Cycle 2 Day 1 due to lack of adequate

recovery of KRT-232 (AMG 232) +KRD-related toxicities will be considered a DLT.

Subjects who receive < 75% of the planned study drug doses during the first cycle of (i.e. $\leq 5/7$ daily doses of KRT-232 (AMG 232) will be considered non-evaluable for purposes of determining the MTD (unless due to a DLT) and will be replaced. Subjects who experience a DLT during the DLT-evaluable period will be considered evaluable for the purposes of determining the MTD as per Section 13.1.4

Management and dose modifications associated with the above adverse events are outlined in Section 6.

Dose escalation will proceed within each cohort according to the following scheme. Dose-limiting toxicity (DLT) is defined above.

Number of Subjects with DLT at a Given Dose Level	Escalation Decision Rule
0 out of 3	Enter 3 subjects at the next dose level.
≥ 2	Dose escalation will be stopped. This dose level will be declared the maximally administered dose (highest dose administered). Three (3) additional subjects will be entered at the next lowest dose level if only 3 subjects were treated previously at that dose.
1 out of 3	Enter at least 3 more subjects at this dose level. If 0 of these 3 subjects experience DLT, proceed to the next dose level. If 1 or more of this group suffer DLT, then dose escalation is stopped, and this dose is declared the maximally administered dose. Three (3) additional subjects will be entered at the next lowest dose level if only 3 subjects were treated previously at that dose.
≤ 1 out of 6 at highest dose level below the maximally administered dose	This is generally the recommended phase 2 dose. At least 6 subjects must be entered at the recommended phase 2 dose.

5.7. Dose Expansion Cohorts:

Once the RP2D is reached, a goal of 10 additional subjects will be treated at this dose. For the expansion cohort, subjects will continue to be monitored for occurrence of DLT. If 2 of the first 5 subjects or if ≥ 4 of 10 subjects experience DLT, the Principal Investigator will discuss with all study investigators and with CTEP whether further addition of subjects is needed to re-assess the RP2D. When the first 5 additional patients are enrolled in the expansion phase, with a total of 11 patients including the 6 patients who had been already treated at the RP2D, the probabilities of observing 3 or more patients with DLT are 22.1%, 68.7% and 96.7% if the true toxicity rate are 15%, 30%, and 50%. When all 10 additional patients are enrolled in the expansion phase, with a

total of 16 patients including the 6 patients who had been already treated at the RP2D, the probabilities of observing 5 or more patients with DLT are 7.9%, 55%, and 96.2% if the true toxicity rate are 15%, 30%, and 50%. Monitoring of all safety and toxicity data is done by the Principal Investigator and the Corresponding Organization on a real-time basis as data are entered into Medidata Rave using the Web Reporting Module. All participating sites are expected to notify the Principal Investigator when a DLT has occurred.

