2.6. Rationale of KRd + KRT-232 (AMG 232) Human Dosing

Dosing for the KRd backbone for the current proposed study is modeled after the Phase 3 ASPIRE study as described in Section 2.4, which was based on an earlier Phase 1 study where the MTD was not reached for KRd dosing (Niesvizky et al., 2013). Hence, KRd at these dose levels (carfilzomib 27 mg/m², lenalidomide 25 mg, and dexamethasone 40 mg) has an acceptable and well-studied safety profile. In practice, carfilzomib is often given at higher doses (36 mg/m²) in combination with lenalidomide and dexamethasone, based on a phase 1/2 study of KRd in newly diagnosed multiple myeloma (Jakubowiak et al., 2012), which gives added confidence that the addition of KRT-232 (AMG 232) to the KRd backbone at its standard dosing will be feasible from a safety and tolerability standpoint.

Although the MTD of KRT-232 (AMG 232) was defined at 240 mg QD for 7 days on a 21-day cycle in the first-in-human (FIH) study of KRT-232 (AMG 232) in solid tumors (Section 2.2), the starting dose level of KRT-232 (AMG 232) for the current study will begin at 60 mg 7 days on a 28-day cycle to carefully evaluate for overlapping toxicities such as thrombocytopenia with the KRd backbone. Dose-escalation will occur using a standard 3+3 design with increasing dose levels of KRT-232 (AMG 232) at 90 mg, 120 mg, 180 mg, and 240 mg 7 days on a 28-day cycle, with the highest planned dose level 5 being comparable to the MTD in the first-in-human trial of KRT-232 (AMG 232) monotherapy. Using this standard 3+3 design, a DLT rate less than 33% would be considered acceptable.

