5.4. KRT-232 (AMG 232) + Carfilzomib, Lenalidomide, and Dexamethasone Treatment Plan

Dose Regimen

KRT-232 (AMG 232) + carfilzomib, lenalidomide, and dexamethasone will be administered per the following schedule:

Cycles 1-12 (28 day cycle)

- KRT-232 (AMG 232) once daily by mouth 7 out of 28 days
- Carfilzomib 20 mg/m² IV on Days 1 and 2 of Cycle 1, escalating to 27 mg/m² IV on Days 8, 9, 15, 16 of Cycle 1 and continuing on Days 1, 2, 8, 9, 15, 16 of Cycles 2 through Cycle 12
- Lenalidomide 25 mg PO on Days 1-21
- Dexamethasone 40 mg PO or IV on Days 1, 8, 15, and 22

Cycles 13-18 (28 days each)

- KRT-232 (AMG 232) once daily by mouth 7 out of 28 days
- Carfilzomib 27 mg/m² IV on Days 1, 2, 15, and 16
- Lenalidomide 25 mg PO on Days 1-21
- Dexamethasone 40 mg PO or IV on Days 1, 8, 15, and 22

Cycles 19+ (28 days each)

- KRT-232 (AMG 232) once daily by mouth 7 out of 28 days
- Lenalidomide 25 mg PO on Days 1-21
- Dexamethasone 40 mg PO or IV on Days 1, 8, 15, and 22

Part A (Dose-escalation scheme)

The MTD is defined as the highest dose at which six subjects have been treated and less than two subjects experienced DLT within the first cycle of treatment in Phase I of the trial. To determine the MTD, escalation for KRT-232 (AMG 232) will be conducted following the “3+3” design with de-escalation. A cohort of three subjects will be treated at the starting dose level and observed until the end of the first cycle (subjects non-evaluable for DLT will be replaced). The dose level will be escalated with each new cohort until at least one out of three subjects of a cohort experiences DLT. If one subject experiences a DLT, then three additional subjects will be treated at the same dose level; if none of the three additional subjects experiences a DLT, then the dose escalation will be continued by treating the next cohort of three subjects at the next higher dose level. If at least two out of up to six subjects at a dose level experience a DLT, the MTD will be considered to have been exceeded, and up to 3 more subjects will be treated at the next lower dose if there are less than 6 subjects already treated at that dose. The dose steps for escalation are displayed below:

Dose Escalation Schedule	
Dose Level	Dose of KRT-232 (AMG 232)*
- 1	30 mg/day PO x 7 days out of 28 day cycle
+ 1	60 mg/day PO x 7 days out of 28 day cycle
+ 2	90 mg/day PO x 7 days out of 28 day cycle
+ 3	120 mg/day PO x 7 days out of 28 day cycle

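### The DLT list gives no single classification for some short-lived grade 3 events: they meet the general non-hematological criterion but not their own duration criterion, and no visible text says which governs

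*Combined protocol and SAP*

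**What the plan says.** The non-hematological DLT criteria appear as the same list in the synopsis and in Section 5.6. The bullets that matter are:

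- **General bullet.** Grade 3 or higher "non-hematological toxicity (excluding increased serum creatinine, or electrolyte abnormalities that are not clinically significant and require no treatment"). No duration is attached, and creatinine and minor electrolyte changes are the only exclusions.
- **Gastrointestinal bullet.** Grade 3 or higher "nausea, vomiting or diarrhea lasting longer than 72 hours despite optimal medical support".
- **Fatigue bullet.** "Grade 3 fatigue persisting > 7 days".
- **Electrolyte bullet.** "Any grade 3 electrolyte abnormalities that do not resolve to grade" 2 or lower within 72 hours.
- **Residual bullet.** "Any other grade 3 or 4 non-hematologic toxicities not predefined above will be considered a DLT".

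The list also has an acute kidney injury bullet, defined by creatinine and limited to injury lasting more than 72 hours. Separately, the synopsis, Section 5.4 and the opening of Section 6 treat a subject who needs a dose reduction in Cycle 1 as having a DLT.

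The DLT count drives the cohort decisions. Section 5.4 states: "The MTD is defined as the highest dose at which six subjects have been treated and less than two subjects experienced DLT". In the Section 5.6 decision table, when one of three subjects has had a DLT and three more are treated: "If 1 or more of this group suffer DLT, then dose escalation is stopped, and this dose is declared the maximally administered dose". Section 2.6 adds: "Using this standard 3+3 design, a DLT rate less than 33% would be considered acceptable".

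**The concern.** The general bullet and the duration bullets overlap, and nothing visible ranks them. If the bullets are alternatives, any one of which suffices, the gastrointestinal and fatigue time limits can never change a classification. If the specific bullets govern the events they name, the general bullet lacks the exception it needs. Either way, some of the text does not do what it appears to be there to do.

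What is at stake is the MTD. Decisions rest on three to six subjects per level, so one event counted by one site or cohort and not by another can alter the path of escalation. The same call can also decide evaluability: Section 5.6 replaces a subject who took five or fewer of the seven KRT-232 doses, unless a DLT was the reason. The events are not remote ones, since Section 2.3.2 lists diarrhea, nausea, vomiting and fatigue among the main drug-related adverse events.

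**Working it through.** **1. Apply each bullet to the same event.** Assume a Cycle 1 event with no clear alternative cause and no dose reduction required.

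| Event | General bullet | Its own bullet | Conflict? |
|---|---|---|---|
| Grade 3 diarrhea for 24 h | met | not met | yes |
| Grade 3 fatigue for 2 days | met | not met | yes |
| Grade 3 hypokalemia, treated, grade 2 or lower by 48 h | met | not met | yes |
| Grade 3 electrolyte change, insignificant and untreated, resolved within 72 h | excluded | not met | no |
| The same, unresolved at 72 h | excluded | met | no; the electrolyte bullet does work of its own |
| Creatinine-defined kidney injury, 72 h or less | excluded | not met | no |

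The conflict is therefore confined to the first three rows and events like them.

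**2. Look for a rule of precedence.** The qualifier in the residual bullet hints that named events follow their own criteria, but it limits only that bullet, and the general bullet has already caught the brief event. Sections 5.4, 5.7, 13.1.4 and 13.2.1 use the DLT count without settling the overlap. The visible part of Section 6 does not settle it either. Parts of Sections 6.3 and 6.4 are blacked out, so nothing can be said about those.

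**3. Effect of one reclassified event.**

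| Count | Observed rate | Action |
|---|---|---|
| 0/3 to 1/3 | 0% to 33.3% | three more subjects instead of escalation |
| 1/3 to 2/3 | 33.3% to 66.7% | stop instead of expanding the level |
| 1/6 to 2/6 | 16.7% to 33.3% | stop instead of escalation; the level no longer meets the MTD definition |

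The last row also crosses the limit in Section 2.6: 16.7% is below 33%, and 33.3% is not. In Part B, moving from 1/5 to 2/5 or from 3/10 to 4/10 reaches the Section 5.7 trigger, which prompts a discussion with the investigators and CTEP and does not stop enrollment.

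**4. The plan's own figures.** The Section 5.7 probabilities are exact binomial tails and reproduce. For 3 or more of 11 they are 22.12%, 68.73% and 96.73% at true rates of 15%, 30% and 50%. For 5 or more of 16 they are 7.91%, 55.01% and 96.16%. They take the true DLT rate as given, so this point does not affect them.

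**5. Illustration only.** Let p be the DLT probability when the duration bullets govern. Let q be the share of the remaining subjects whose only qualifying event is a short-lived one. Assume independence. When the general bullet governs, the DLT probability is p' = 1 − (1 − p)(1 − q). The chance of escalating past one 3+3 level is (1 − p)³ + 3p(1 − p)⁵, with p' in place of p for the general reading. Both p and q are assumed; the documents give neither.

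| p | p' at q = 5% to 15% | Chance of escalating, duration reading | Chance of escalating, general reading |
|---|---|---|---|
| 10% | 14.5% to 23.5% | 90.6% | 82.4% to 63.2% |
| 15% | 19.3% to 27.8% | 81.4% | 72.5% to 54.1% |
| 20% | 24.0% to 32.0% | 70.9% | 62.2% to 45.4% |

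The nearest data are the grade 3 or higher rates on KRd in Section 7.1: fatigue 21/392 (5.4%), hypokalemia 22/392 (5.6%), diarrhea 7/392 (1.8%) and nausea 1/392 (0.3%). They cover cycles 1 to 12 without KRT-232 and give no durations, so they do not fix q.

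**The case against.** The strongest reply is that the list yields one answer. No bullet says that a shorter event is not a DLT. Read literally, meeting any criterion is enough, so brief grade 3 diarrhea is a DLT and the duration bullets are merely redundant. This stands in part: the second answer is inferred from the time limits, and a reader who takes the plan to contain two explicit contrary rulings goes beyond the text. But the time limits, together with the residual bullet's wording, make the opposite intent just as plausible, and the plan does not choose.

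A reader might also infer that the whole non-hematological list is in conflict. It is not. The electrolyte and acute kidney injury bullets catch events that the general bullet excludes, and those fit together.

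The Cycle 1 dose-reduction rule settles some cases, since an event that requires a reduction counts under either reading. This narrows the problem without removing it.

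Oversight limits inconsistent application. Sites report DLTs to the Principal Investigator (Section 5.7), who signs off every dose decision and holds at least monthly calls with the investigators and CTEP (Section 12.1). That helps consistency but supplies no written rule.

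Finally, one reclassified DLT matters in any 3+3 design, so step 3 shows sensitivity and not frequency. That is correct.

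**Conclusion.** The point holds for short-lived grade 3 or higher nausea, vomiting or diarrhea, for short-lived grade 3 fatigue, and for treated or clinically significant grade 3 electrolyte abnormalities that resolve within 72 hours. For these, the definition behind a primary objective does not give a determinate classification in the visible text.

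The size is one cohort action per reclassified event. At a six-subject level, that single event separates a dose that meets the MTD definition from one that does not. The frequency is unknown, and the illustrative probabilities rest on assumed rates. The documents do not support an inference that any dose decision was wrong or that the MTD is biased in a given direction, because they report no trial events and do not say which reading was applied.

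**What to change.** The sponsor should reconcile the non-hematological bullets in the synopsis and Section 5.6 so that every event has one classification. The text should say whether the bullets are alternatives or, if not, which one governs when two apply. It should cover every grade of the named events, including any grade 4 fatigue or grade 4 electrolyte abnormality, because the specific bullets for those events name grade 3 only.

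Two shortcuts would create new gaps. Deleting the specific bullets would drop the electrolyte and kidney injury criteria that catch events the general bullet excludes. Exempting every event that has its own criterion would leave those grade 4 events unclear.

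The rule should be fixed without regard to dose decisions already made and applied uniformly across sites and cohorts. If Cycle 1 events have been collected, those classified differently under the two readings should be listed, with a note on whether a cohort decision would change. No view is taken on which clinical rule is right.

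The cost is a short wording amendment and an event review. The downside is that a cohort decision may have to be revisited, for example with three more subjects at a level if 0/3 becomes 1/3.
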